5.4 Other Modalities or Procedures

No other modalities or procedures will be used in this protocol

5.5 Duration of Therapy

In the absence of treatment delays due to adverse events, treatment may continue until any one or more of the following criteria apply:

- Disease progression
- Inter-current illness that prevents further administration of treatment
- Unacceptable adverse event(s)
- Patient voluntarily withdraws from treatment
- General or specific changes in the patient's condition that render the patient unacceptable for further treatment in the judgment of the treating investigator **OR**
- Investigator determination that the patient is no longer benefitting from protocol therapy.

If treatment is stopped due to one or more of the criteria above, both enzalutamide and IONIS-AR-2.5_{Rx} ASO will be discontinued.

5.6 Off Treatment Criteria

Patients will be removed from protocol specified therapy when any of the respective criteria listed in Section 5.5 apply.

Document in the source the reason for ending protocol therapy and the date the patient was removed from treatment.

All patients who discontinue treatment should comply with protocol specific follow-up procedures. The only exception to this requirement is when a subject withdraws consent for all study procedures or loses the ability to consent freely.

5.7 Duration of Follow-Up

Patients will be followed for up to 24 months after removal from treatment or until death, whichever occurs first. Patients removed from treatment for unacceptable adverse events will be followed until resolution or stabilization of the adverse events.

5.8 Off Study Criteria

Patients can be taken off study at any time at their own request, or they may be withdrawn at the discretion of the investigator for safety, behavioral or administrative reasons. The reason(s) for discontinuation from study will be documented and may include:

- 5.8.1** Patient withdraws consent (termination of treatment and follow-up);
- 5.8.2** Loss of ability to freely provide consent through imprisonment or involuntary incarceration for treatment;
- 5.8.3** Patient is unable to comply with protocol requirements;
- 5.8.4** Treating physician determines continuation on the study would not be in the patient's best interest;
- 5.8.5** Development of second malignancy (except for basal cell carcinoma or squamous cell carcinoma of the skin) that requires treatment, which would interfere with this study;
- 5.8.6** Lost to Follow-up. If a research subject cannot be located to document survival after a period of 2 years, the subject may be considered "lost to follow-up." All attempts to contact the subject during the two years must be documented;
- 5.8.7** Termination of the study by the University of Michigan;
- 5.8.8** Patient completes protocol treatment and follow-up criteria.

5.9 Patient Replacement

Patients who do not receive any dose of the study drug IONIS-AR-2.5_{RX} will be replaced.

6.0 STUDY PROCEDURES

Time and Events Table

All assessments have a window of \pm 3 business days except for imaging/tumor measurements where a window of \pm 7 business days will apply or unless otherwise specified.

Cycle length = 21 days

Trial period	Screening	Treatment								Safety Follow-up/EOT	Follow-up Visits
Treatment Cycle/Title	Screening Visit	Cycle 1								30 days from last dose of IONIS-AR-2.5Rx (+/- 7 business days)	Every 12 weeks (+/- 7 business days) For up to 24 months
Scheduling Window (Days)	-28 to -1	D 1	D 4	D 8	D 11	D 15	D 1	D 8	D 15		
Administrative Procedures:											
Informed Consent	X										
Review Eligibility Criteria	X										
Demographics and Medical History	X	X	X	X	X	X	X	X	X		
Prior and Concomitant Medications	X	X	X	X	X	X	X	X	X		
Survival Status											X ⁶
Clinical Assessments:											
Review Adverse Events	X	X	X	X	X	X	X	X	X		
Physical Examination	X	X		X		X	X				
Vital Signs		X	X	X	X	X	X	X	X		
Height ⁵ , Weight	X	X					X				X
ECOG Performance Status	X	X					X				X
Laboratory Assessments:											
PT/INR and PTT/aPTT	X	X		X		X	X	X	X		
CBC with differential, platelets	X	X	X	X	X	X	X	X	X		
Comprehensive Metabolic Panel ¹ , D-dimer	X	X	X	X	X	X	X	X	X		
PSA	X	X					X			X	X
Testosterone	X	X								X	
TSH, free T3, free T4 (If Clinically Indicated: FSH, LH, ACTH)	X									X	
Treatment:											
IONIS-AR-2.5Rx ⁴		X	X	X	X	X	X	X	X		
Enzalutamide		PO daily in 21-day cycles									

Trial period	Screening	Treatment								Safety Follow-up/EOT	Follow-up Visits
Treatment Cycle/Title	Screening Visit	Cycle 1								30 days from last dose of IONIS-AR-2.5Rx (+/- 7 business days)	Every 12 weeks (+/- 7 business days) For up to 24 months
Scheduling Window (Days)	-28 to -1	D 1	D 4	D 8	D 11	D 15	D 1	D 8	D 15		
Imaging Tumor Assessments²											
CT chest/CXR	X									X	X
MRI Abdomen/Pelvis or CT Abdomen/Pelvis	X									X	X
Bone Scan	X									X	X
QoL questionnaires³		X					X			X	
Correlatives											
Whole blood for banking		X pre-dose									
Tumor Tissue Archival CRPC	X										
Tumor Tissue Biopsy ⁷	X							X		X	
PK Plasma IONIS-AR-2.5Rx concentration (pre-dose) ^{8,10}		X	X	X	X	X	X	X			
PK Plasma IONIS-AR-2.5Rx concentration (end of infusion) ^{8,9,10}		X	X	X	X	X	X	X			

1. Comprehensive metabolic panel (CMP) to include: albumin, alkaline phosphatase, ALT/SGPT, AST/SGOT, BUN, creatinine, electrolytes (sodium, potassium, calcium, chloride, bicarbonate), glucose, and total bilirubin; LDH, D-dimer.
2. Imaging Assessments: Every 12 weeks or as clinically indicated.
3. QoL questionnaires: FACT-P and EuroQoL-5D.
4. Starting Cycle 1 Day 1, all subjects should take ASA 81 mg PO q day unless contraindicated.
5. Height only at baseline.
6. Survival status every 6 months.
7. Tumor Tissue Biopsy at Screening is required only if Archival Tissue is not available. Tissue biopsy collection at post cycle 2 and Safety Follow-up/EOT is optional if subject consents; +/- 7 working days.
8. Plasma PK samples may also be used for profiling of drug binding proteins, bioanalytical method development and/or validation purposes, stability assessments, metabolite assessments, immunogenicity assessments or to assess other actions of IONIS-AR-2.5Rx with plasma constituents.
9. Collected within 2 minutes before infusion is stopped
10. Collected Cycle 1 Days 1, 4, 8, 11 and 15 and Cycle 2 Day 1, 8 and 15 only.

7.0 MEASUREMENT OF EFFECT

7.1 Antitumor Effect- Solid Tumors

Response and progression will be evaluated in this study using the new international criteria proposed by the Response Evaluation Criteria in Solid Tumors (RECIST) Committee [JNCI 92(3):205-216, 2000]. Changes in only the largest diameter (unidimensional measurement) of the tumor lesions are used in the RECIST v1.1 criteria.

7.1.1 Definitions

Evaluable for toxicity. All patients will be evaluable for toxicity from the time of their first treatment with IONIS-AR-2.5Rx.

Evaluable for PSA response. Only those patients who have received at least 1 dose of IONIS-AR-2.5Rx, and have at least 2 PSA measures at least 1 week apart after initiating treatment will be considered evaluable for PSA response. (Note: Patients who exhibit objective disease progression prior to the end of cycle 2 will also be considered evaluable and will be classified as PSA non-response).

Evaluable for objective response. Only those patients who have measurable disease present at baseline, have received at least 1 dose of IONIS-AR-2.5Rx, and have had their disease re-evaluated will be considered evaluable for objective response. These patients will have their response classified according to the definitions stated below. (Note: Patients who exhibit objective disease progression prior to the end of cycle 4 will also be considered evaluable).

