11.1 Study Design

Dose Assignment in Phase 1b: The first patient will be enrolled to dose level 3 of IONIS-AR-2.5_{Rx}, in combination with a fixed dose of enzalutamide. Subsequent dose assignments to dose levels 1, 2 or 3 will be based upon the statistical-model-based TITE-CRM design. This trial will seek to estimate the MTD, the true value of which is defined as the dose level with probability of DLT closest to but not exceeding 35%.

Final Efficacy Analysis After all 35 evaluable patients are enrolled and the PSA response endpoint is recorded for all patients, we will fit the Bayesian isotonic regression model on all patients' data. If the probability that the PSA response rate at the final estimated dose exceeds 5% is at least 0.95, the trial will have successfully completed its primary objective.

Interim Analysis/Criteria for Stopping Study Continuous monitoring of safety is built into the TITE-CRM model, and the trial will stop at any point in which all dose levels have a model-estimated probability of DLT exceeding 37.5%.

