11.4 Analysis Datasets

All subjects who enroll and receive at least one dose of each treatment in the combination therapy will be used for updating the TITE-CRM model. Patients who withdraw prior to completing their DLT window and without the occurrence of DLT will have their likelihood contribution downweighted as described in the first paragraph of Section 11.6.1 and will be replaced.

All subjects who have completed one or more cycles of treatment or who are removed from protocol due to progression or toxicity will be evaluable in the efficacy analyses.

Population	Definition
Enrolled	This will comprise all subjects who meet the eligibility criteria and are registered onto the study.
Evaluable	This will comprise all subjects who receive at least one cycle of treatment or who are removed from protocol due to progression or toxicity.
Intention-to-treat (ITT)	This will comprise all subjects who meet the eligibility criteria and are registered onto the study irrespective of their compliance to the planned course of treatment. (See ITT principle below*).
Per Protocol Set (Valid Cases, Efficacy Sample, Evaluable Subjects Sample)	This will comprise all subjects who completed at least one cycle of protocol therapy and have a post-baseline PSA drawn.
Safety	This will comprise all subjects who receive any protocol treatment.
Treated	This will comprise all subjects who have been exposed to the planned course of treatment to any extent.

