Efficacy Analysis The efficacy analysis will occur in the PSA response evaluable dataset after the patients have their PSA Response endpoint recorded. Let $\{m_1, m_2, m_3\}$ denote the true, unknown probability that a patient exhibits PSA response at the three dose levels of IONIS-AR-2.5_{Rx} (with fixed dose of enzalutamide), respectively. We will use weakly informative, independent Beta prior distributions: $m_1 \sim \text{Beta}(0.1, 1.9)$, $m_2 \sim \text{Beta}(0.3, 1.7)$, and $m_3 \sim \text{Beta}(0.5, 1.5)$, or the information equivalent of 2 historical patients' worth of data at each dose level, with historical response rates of 0.05, 0.15, and 0.25, respectively. The posterior distributions will also be Beta: add the number of PSA responders at each dose level to the first shape parameter (0.1, 0.3, or 0.5), and add the number of PSA non-responders at each dose level to the second shape parameter (1.9, 1.7, or 1.5). So, for example, if 4 patients received dose level 1, and one of these patients exhibited a PSA response, then posterior Beta distribution for m_1 would be Beta (0.1+1, 1.9+3) = Beta (1.1, 4.9). We will then independently sample a large number, e.g., 200,000, of draws from each of these posterior Beta distributions. In order to preserve the isotonic assumption that the potential for response is not decreasing with dose level, we will only keep posterior samples satisfying $m_1 \leq m_2 \leq m_3$. To estimate the Bayesian probability that the response rate at the MTD exceeds 5%, we will calculate the proportion of isotonic draws at the m_i exceeding 0.05, where dose level i is the estimated MTD. We will calculate the Bayesian probability that the probability of PSA response at the final estimated MTD exceeds 5%. If the proportion of posterior draws at the estimated MTD exceeding 0.05, subject to the isotonic constraint, is at least 0.95, the trial will have successfully completed its primary objective.

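### The denominator of the primary PSA-response analysis is stated inconsistently, and the two-PSA evaluability rule can only remove non-responders, which can change the success call near its boundary

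*Combined protocol and SAP*

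**What the plan says.** The protocol describes the patients in the primary PSA analysis in several places.

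- **7.1.1:** patients must have had at least one dose of IONIS-AR-2.5Rx and "have at least 2 PSA measures at least 1 week apart after initiating treatment will be considered evaluable for PSA response". The one exception is that patients with "objective disease progression prior to the end of cycle 2 will also be considered evaluable", as non-responders.
- **11.4, text and Evaluable row:** subjects with one or more cycles, or "who are removed from protocol due to progression or toxicity will be evaluable in the efficacy analyses".
- **11.4, Per Protocol Set:** subjects who "completed at least one cycle of protocol therapy and have a post-baseline PSA drawn". The row gives no exception, and its label also calls it the efficacy sample and the evaluable subjects sample.
- **11.6.1:** "The efficacy analysis will occur in the PSA response evaluable dataset". That name is not in the 11.4 table. It matches the term in 7.1.1, and 11.0 likewise refers to response-evaluable patients.
- **11.1 (and the synopsis):** "we will fit the Bayesian isotonic regression model on all patients' data".

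Section 7.2.2 defines a PSA response as a decline of 50% or more, measured twice at least 3 weeks apart. Except for early objective progression in 7.1.1, no section says that a treated patient with too few PSA values counts as a non-responder.

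**The concern.** The success criterion is one posterior probability compared with 0.95, computed from responders and non-responders at each dose level. Whoever is left out of the non-responder count moves that probability. Here the rules put the same patient in or out depending on the section read, and in an open-label trial the choice could be made after the results are known.

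The direction is also not neutral. A patient who dies, withdraws or is lost before a second post-treatment PSA cannot meet 7.2.2. Excluding that patient removes a non-responder and never a responder.

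**Working it through.** **1. The same patient under each rule.**

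| Patient | 7.1.1 | 11.4 Evaluable | 11.4 Per Protocol | 11.1 |
|---|---|---|---|---|
| Stops in cycle 1 for toxicity, one later PSA | out | in | out | in |
| Stops in cycle 1 for toxicity, two PSAs in follow-up | in | in | out | in |
| Completes cycle 1, one PSA, then withdraws | out | in | in | in |
| Objective progression in cycle 1, no PSA | in | in | out | in |
| Dies in cycle 1, not recorded as progression or toxicity | out | out | out | in |

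No two columns agree throughout.

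**2. Inputs and formula (11.6.1).** The priors are Beta(0.1, 1.9), Beta(0.3, 1.7) and Beta(0.5, 1.5) for levels 1 to 3. With r_j responders among n_j patients, the posterior is m_j ~ Beta(a_j + r_j, b_j + n_j − r_j). Success requires Pr(m_i > 0.05 | m_1 ≤ m_2 ≤ m_3) ≥ 0.95, where i is the estimated MTD.

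**3. The plan's own figure.** I take the Table 1B cell with DLT rates {8%, 13%, 25%} and response rates {5%, 13%, 20%}, which states 0.92. Simulating the TITE-CRM as specified, with all 35 patients counted and 1,500 trials, gives 0.903. Over the 28 cells, 18 agree within 2 points. The rest differ by at most about 0.07, within 3 standard errors of the plan's 250-trial runs. The stated operating characteristics are thus consistent with a full denominator and no missing PSA.

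**4. Effect on the success call.** Dropped patients are non-responders at the MTD level. The values come from numerical integration.

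| Allocation (levels 1/2/3) | Responders | MTD | All 35 counted | After dropping |
|---|---|---|---|---|
| 5/10/20 | 0/1/2 | 3 | 0.949, fail | 1 dropped: 0.955, pass |
| 35/0/0 | 5/0/0 | 1 | 0.941, fail | 2 dropped (5/33): 0.951, pass |
| 0/35/0 | 0/4/0 | 2 | 0.912, fail | 7 dropped (4/28): 0.954, pass |
| 0/0/35 | 0/0/3 | 3 | 0.880, fail | 9 dropped (3/26): 0.946, fail; 10 dropped (3/25): 0.952, pass |

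In the first row the posteriors are Beta(0.1, 6.9), Beta(1.3, 10.7) and Beta(2.5, 19.5). Dropping one patient changes the last to Beta(2.5, 18.5). The second and third rows are limiting cases, because the first patient always starts at level 3. With 4 of 35 at level 3 the probability is 0.961, which passes with everyone counted.

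The observed rates move with the denominator: 5/35 = 14.3% against 5/33 = 15.2%, and 3/35 = 8.6% against 3/25 = 12.0%.

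**5. Effect on the probability of success.** The scenario is DLT {8%, 13%, 25%}. The early-leaver shares are assumptions, since the documents give none. Each pair is leavers counted as non-responders against leavers dropped.

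| True response | 10% leave | 20% leave | Every DLT patient leaves |
|---|---|---|---|
| {3%, 8%, 10%} | 0.36 / 0.37 | 0.27 / 0.35 | 0.24 / 0.35 |
| {5%, 13%, 20%} | 0.86 / 0.87 | 0.78 / 0.83 | 0.74 / 0.81 |

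For {20%, 28%, 35%} under the same DLT rates the gap is 1 point or less. Over all 28 cells it is about 0 to 3 points at 10%, up to about 8 at 20%, and up to about 15 if every DLT patient is dropped.

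**The case against.** The best defence is that the plan does name its set. Section 11.6.1 and 11.0 point to the term defined in 7.1.1, and 11.6.1 never calls on the Per Protocol Set. On that view only untidy labels remain. This is partly right: listing a Per Protocol Set does not make it primary. But the 11.4 sentence about efficacy analyses and the 11.1 wording still contradict 7.1.1, and 7.1.1 itself has the one-directional exclusion.

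A reader might infer that 7.1.1 drops everyone who stops for toxicity. It does not. The events table schedules PSA at the Safety Follow-up/EOT visit and marks it at the 12-weekly follow-up visits, and 5.6 asks patients who discontinue treatment to comply with follow-up. A patient who stops in cycle 2 can have the cycle 2 day 1 value and the EOT value. One who stops in cycle 1 can have the EOT value and the first follow-up value. A DLT is also not the same as leaving, because 5.2 often provides for a hold and a reduced dose. Nor does 11.4 rescue everyone that 7.1.1 loses, as the last row of the first table shows.

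A reader might also infer that the reported rate is inflated. The documents support only that it can be, because they give no early-leaver rate. Nor does the gap between the 1-week spacing in 7.1.1 and the 3-week spacing in 7.2.2 add inflation: a patient whose only two values are 1 week apart is kept and counts as a non-responder.

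**Conclusion.** The denominator conflict stands and should be fixed before the efficacy analysis. Under 7.2.2 the two-PSA rule can bias the response rate upward and cannot bias it downward. Near the boundary one or two patients can decide the call, but in other configurations seven or ten are needed, and with clearly effective treatment in the safest DLT scenario the effect is 1 point or less.

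This rests on three things. The confirmed definition in 7.2.2 must govern: 2.4.2 and 11.2.1 speak of a decline at any time without repeating the confirmation, and if a single value sufficed the direction would no longer be guaranteed. The early-leaver shares of 10% and 20% are assumed. The simulations take response as independent of DLT. The point is a should-fix and does not invalidate the design.

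**What to change.** Define one primary efficacy set: every patient who received at least one dose of IONIS-AR-2.5Rx. Count any patient without a documented response under 7.2.2, for any reason including no post-baseline PSA, as a non-responder. Delete the two-PSA requirement from 7.1.1, and use the same set in the synopsis, 7.1.1, 11.0, 11.1, 11.4 and 11.6.1.

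State that a patient replaced under 11.4 stays in this denominator if dosed. Replacement can restore the number enrolled, but it does not restore a lost non-responder. Keep the Per Protocol Set as a sensitivity analysis only, without its efficacy-sample labels.

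The cost is wording in six places and no new data. The reported response rate and the probability of declaring success may be slightly lower.

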7.1.2 Disease Parameters

Measurable disease. Measurable lesions are defined as those that can be accurately measured in at least one dimension (longest diameter in the plane of measurement is to be recorded) with a minimum size of:

- 10mm by CT scan (irrespective of scanner type) for studies with a slice thickness of \leq 5mm or twice the slice thickness or MRI
- 10mm caliper measurement by clinical exam (lesions which cannot be accurately measured with calipers should be recorded as non-measurable)
- 20mm by chest X-ray (if clearly defined and surrounded by aerated lung)

All tumor measurements must be recorded in millimeters (or decimal fractions of centimeters).

Malignant lymph nodes: To be considered pathologically enlarged and measurable, a lymph node must be \geq 15mm in short axis when assessed by CT scan (CT scan slice thickness recommended to be no greater than 5 mm). At baseline and in follow-up, only the short axis will be measured and followed.

Note: Tumor lesions that are situated in a previously irradiated area are not considered measurable.

Non-measurable disease. All other lesions (or sites of disease), including small lesions (longest diameter $<$ 20 mm with conventional techniques or $<$ 10 mm using CT scan), are considered non-measurable disease. Bone lesions, leptomeningeal disease, ascites, pleural/pericardial effusions, lymphangitis cutis/pulmonis, inflammatory breast disease, abdominal masses (not followed by CT or MRI), and cystic lesions are all non-measurable.

Target lesions. All measurable lesions up to a maximum of 2 lesions per organ and 5 lesions in total should be identified as **target lesions** and recorded and measured at baseline. Target lesions should be selected on the basis of their size (lesions with the longest diameter), be representative of all involved organ, but in addition should be those that lend themselves to reproducible repeated measurements.

Lymph nodes merit special mention since they are normal anatomical structures which may be visible by imaging even if not involved by tumor. Pathological nodes which are defined as measurable and may be identified as target lesions must meet the criterion of a short axis of $\geq 15\text{mm}$ by CT scan. Only the short axis of these nodes will contribute to the baseline sum. The short axis of the node is the diameter normally used by radiologists to judge if a node is involved by solid tumor. Nodal size is normally reported as two dimensions in the plane in which the image is obtained (for CT scan this is almost always the axial plane; for MRI the plane of acquisition may be axial, sagittal or coronal). The smaller of these measures is the short axis. For example, an abdominal node which is reported as being $20\text{mm} \times 30\text{mm}$ has a short axis of 20mm and qualifies as a malignant, measurable node. In this example, 20mm should be recorded as the node measurement. All other pathological nodes (those with short axis $\geq 10\text{mm}$ but $< 15\text{ mm}$) should be considered non-target lesions. Nodes that have a short axis $< 10\text{mm}$ are considered nonpathological and should not be recorded or followed.

A sum of the diameters (longest for non-nodal lesions, short axis for nodal lesions) for all target lesions will be calculated and reported as the baseline sum diameters. If lymph nodes are to be included in the sum, then as noted above, only the short axis is added into the sum. The baseline sum diameters will be used as reference to further characterize any objective tumor regression in the measurable dimension of the disease.

Non-target lesions. All other lesions (or sites of disease) including pathological lymph nodes should be identified as non-target lesions and should also be recorded at baseline. Measurements are not required and these lesions should be followed as 'present', 'absent', or in rare cases 'unequivocal progression' (more details to follow). In addition, it is possible to record multiple non-target lesions involving the same organ as a single item on the case record form (e.g. 'multiple enlarged pelvic lymph nodes' or 'multiple liver metastases').

